14 OTHER ASPECTS

14.1 Quality Assurance and Quality Control Procedures

The strategy to ensure data quality and integrity will include remote and/or on-site monitoring and procedures for data management and may include a Quality Assurance (QA) audit.

14.1.1 *Site Monitoring*

The clinical research associate (CRA) is responsible for routine review of the eCRF at regular intervals during the study in order to verify adherence to the protocol and the completeness, accuracy, and consistency of the data collected by the investigator or his/her staff and entered by them in the eCRF. The CRA should have access directly or remotely, as appropriate, to any subject records needed to verify the entries in the eCRF.

The investigator agrees to cooperate with the CRA to ensure that any problems detected through remote or on-site monitoring are resolved.

14.1.2 *Quality Assurance Audits*

Quality Assurance audits might be performed by 1 or more auditors if considered necessary by the sponsor or by the contract research organization (CRO). The QA audits will imply the examination and evaluation of the accuracy of information obtained and collected by the investigator or managed by the CRO. Study facilities and equipment might be also subjected to QA audits.

14.2 Ethical Considerations

The study will be conducted in accordance with the Declaration of Helsinki, Ethical Principles for Medical Research Involving Human Subjects, and applicable GCP principles.

14.3 Regulatory and Ethical Compliance

This protocol, subject information, and ICF, and personal data processing consent, if applicable, will be submitted to an Institutional Review Board (IRB) along with a notification to regulatory authorities according to the local regulations. Notification in writing of ethical approval must be obtained from the IRB by the investigator before study initiation.

Any change or addition to the protocol can only be made in a written protocol amendment that must be approved by the sponsor, IRB, and/or health authority(ies) according to applicable regulations.

The study will be conducted at each approved site under the scientific, clinical, and operative responsibility and supervision of the principal investigator by the medically and scientifically trained qualified person appointed by him/her.

14.4 Subject Information and Consent

Informed consent will be obtained in accordance with the Declaration of Helsinki, ICH GCP, US Code of Federal Regulations (CFR) for Protection of Human Subjects (21 CFR 50.26[a,b], CFR 50.27, and CFR Part 56, Subpart A), and the Health Insurance Portability and Accountability Act.

Before entering the study, written informed consent will be obtained from all subjects.

Investigators are responsible for the correctness of the recruitment procedure and for using comprehensible verbal communication when providing information to subjects.

The investigators will also clearly inform the patient that he/she can leave the study at any time and for any reason without giving an explanation, and that this discontinuation would not in any case deteriorate the patient's relationship with the physician.

This information is exhaustively reported in the information sheet enclosed with the study ICF.

A copy of the ICF, including the information sheet, will be given to the patient, together with any needed clarification. Sufficient time will be given to enable the patient to take a decision whether to participate in the study.

14.5 Subject Confidentiality

Before entering the study, the written informed consent will be obtained from the subjects.

Patient confidentiality is strictly held in trust by the participating investigators, their staff, and the sponsor and their agents. This confidentiality is extended to cover testing of samples in addition to the clinical information relating to participants. Therefore, the study protocol, documentation, data, and all other information generated will be held in strict confidence. No information concerning the study or the data will be released to any unauthorized third party without prior written approval of the sponsor.

Patient will be assigned a unique identifier by the sponsor. Any patient's record or dataset that is transferred to the sponsor will contain the identifier only; the patient's name or any information that would make the participant identifiable will not be transferred.

The patient will be informed that his/her personal study-related data will be used by the sponsor. The level of disclosure will also be explained to the patient. The patient will be informed on the nature of the data, processing mechanisms, period of data retention, and exercising of their rights.

The patient will be informed that his/her medical records may be examined by Clinical Quality Assurance auditors or other authorized personnel appointed by the sponsor, by appropriate IRB members, and by inspectors from regulatory authorities.

A copy of the ICF will be given to the patient, together with any needed clarification. The patient's data will be collected only if informed consent has been obtained in writing.

14.6 Protocol Amendments

Any amendment to this protocol must be approved by AzurRx. Amendments will be submitted to the IRB for written approval. Written approval must be obtained before implementation of the amended version occurs. The written signed approval from the IRB should specifically reference the investigator name, protocol number, study title, and amendment number(s) that is applicable. Amendments that are administrative in nature do not require IRB approval but will be submitted to the IRB for information purposes.

14.7 Registration of the Protocol

In order to ensure that information on clinical trials reaches the public in a timely manner and to comply with applicable law, regulation, and guidance, the protocol will be registered in and publicly disclosed on ClinicalTrials.gov.

14.8 Study Report and Communication of Results

A clinical study report will be prepared according to standards set out in the ICH Guideline for Structure and Content of Clinical Study Reports (ICH E3) and provided to the regulatory agency(ies), regardless of the use or otherwise of these results for regulatory purposes.

AzurRx is committed to report at scientific meetings or to publish the results of the study in a complete and transparent manner, following the recommendations of the International Committee of Medical Journal Editors.

The results of the study, or any part thereof, shall not be published without the prior review or written consent and approval of AzurRx, and such consent and approval is not to be unreasonably withheld. However, no communication or publication will include AzurRx's confidential information.

AzurRx will register the study on a publicly accessible website (eg, ClinicalTrials.gov or EudraCT) in accordance with applicable laws and regulations.

16 APPENDICES

[Appendix A - Schedule of Assessments](#)

[Appendix B - Bristol Stool Scale](#)

[Appendix C - WHO Ordinal Scale for Clinical Improvement](#)

16.1 Appendix A - Schedule of Assessments

Visit ¹	Screening ²	Treatment				Follow-up					
						Short-term				Long-term	
Timing (D=day, M=month)	D -3 to -1	D1	D4	D8	D15	D22	D29	D36	D43	M4	M6
Deviation vs randomization day			±1 day	±1 day	±2 days	±2 days	±2 days	±3 days	±3 days	±1 week	±1 week
Informed consent	X										
Eligibility (inclusion/exclusion criteria)	X	X									
Demography	X										
Medical history (or changes)	X	X	X	X	X	X	X	X	X		
Pregnancy test (urine or serum)	X				X						
Stool analysis	X										
Stool sample for SARS-CoV-2 RNA ³	X	X	X	X	X	X	X	X	X		
Diarrhea clinical assessment	X	X	X	X	X	X	X	X	X		
Nasopharyngeal swab for SARS-CoV-2 RNA ³	X	X	X	X	X	X	X	X	X		
Laboratory assessments ⁴ (L=local, C=central)	L	C		C	C		C		C		
Overall clinical assessment ⁵	X	X	X	X	X	X	X	X	X		
Randomization		X									
Dosing study drug		Daily TID, with last dose on D14 or 15									
Daily diary		Daily									
Adverse events	X	X	X	X	X	X	X	X	X		
Concomitant medications		X	X	X	X	X	X	X	X		
Survival status										X	X
Persistence of COVID-19 symptoms										X	X
Recurrence of COVID-19 symptoms										X	X
(Re)Hospitalization due to COVID-19										X	X

- ¹ Patients may be hospitalized, inpatient in a research unit, or seen in an outpatient clinic or in a home care setting.
 - ² Screening may occur on the same day as randomization, if all procedures may be completed. If they occur on the same day, procedures scheduled for both visits are not required to be duplicated.
 - ³ At screening, eligibility can be determined by local SARS-CoV-2 viral RNA analysis on a nasopharyngeal swab. Only one screening sample is required and can be determined by local requirements. Eligibility can be determined at a local laboratory at screening; however, a central laboratory may be used at screening if needed. On Days 1 to 43, the nasopharyngeal swab and stool sample will be collected and sent to the central lab.
 - ⁴ Local laboratory testing at screening should include at least AST, ALT, and serum creatinine to determine eligibility. Central laboratory testing will include CBC, BUN, blood sugar, electrolytes (sodium, chloride, potassium, and bicarbonate [HCO₃]), alkaline phosphatase, AST, ALT, LDH, total bilirubin, serum creatinine, C-reactive protein, and fecal calprotectin. When only central testing is required, any other laboratory assessment may be conducted at the local laboratory for the physician's safety assessment according to the local practice and patient's clinical needs
 - ⁵ Including: mortality; hospital admission and discharge; ICU admission and discharge; WHO severity score and duration, type of administration, vital signs, and quantity of supplemental oxygen treatment. Vital signs should be completed on Days 1-8, 10, and 12 for Part 1 patients, but only need to be recorded in the CRF when the full Overall Clinical Assessment is due at the study visits above.
- * Initial medical history will collect date of initial symptom onset. If date is uncertain, verbatim response from patient will be collected.

16.2 Appendix B - Bristol Stool Scale

Type	Descriptor
Type 1	Separate hard lumps, like nuts (difficult to pass and can be black)
Type 2	Sausage-shaped, but lumpy
Type 3	Like a sausage but with cracks on its surface (can be black)
Type 4	Like a sausage or snake, smooth and soft (average stool)
Type 5	Soft blobs with clear-cut edges
Type 6	Fluffy pieces with ragged edges, a mushy stool (diarrhea)
Type 7	Watery, no solid pieces, entirely liquid (diarrhea)

Source: [Lewis et al., 1997](#).

16.3 Appendix C - WHO Ordinal Scale for Clinical Improvement

Patient State	Descriptor	Score
Uninfected	No clinical or virologic evidence of infection	0
Ambulatory	No limitation of activities	1
Ambulatory	Limitation of activities	2
Hospitalized, Mild Disease	Hospitalized, no oxygen therapy	3
Hospitalized, Mild Disease	Oxygen by mask or nasal prongs	4
Hospitalized, Severe Disease	Non-invasive ventilation or high-flow oxygen	5
Hospitalized, Severe Disease	Intubation and mechanical ventilation	6
Hospitalized, Severe Disease	Ventilation + additional organ support – pressors, RRT, ECMO	7
Dead	Dead	8

A special WHO (2020) committee arrived at the ordinal scale that measures illness severity over time.

SaO ₂	Blood oxygen saturation by pulse oximetry
SAP	Statistical analysis plan
SARS	Severe acute respiratory syndrome
SARS-CoV-2	Severe acute respiratory syndrome coronavirus 2
SD	Standard deviation
SE	Standard error
SoC	Standard of care
SOC	System organ class
TEAE	Treatment-emergent adverse event
TID	3 times per day (ter in die)
WHO	World Health Organization

1. Introduction

The coronavirus disease (COVID-19 2019) is a public health emergency of international concern caused by the severe acute respiratory syndrome coronavirus 2 (SARS CoV-2) virus. An increasing volume of convergent evidence indicates that gastrointestinal (GI) infection and fecal oral transmission of SARS-CoV-2 are important factors in the clinical presentation, virology, and epidemiology of COVID-19. There are currently no approved or investigational treatments with demonstrated clinical efficacy for control of the intestinal SARS-CoV-2 viral shedding and fecal positivity. The evaluation of a safe and effective antiviral agent that is able to potently block SARS-CoV-2 replication in the intestine would address serious unmet medical and epidemiological needs.

To address this unmet need, AzurRx BioPharma Inc. is developing a drug product containing micronized niclosamide in an immediate-release tablet formulation as treatment for SARS-CoV-2 intestinal infection in patients presenting with GI symptoms of COVID-19 disease. Evidence of niclosamide's antiviral properties is sufficient to expect a clinical pharmacodynamic response against viral replication and clinical benefit, justifying the proposed clinical study in COVID-19 patients and favorable benefit-risk assessment.

This statistical analysis plan (SAP) is based upon Section 12 (Statistical Analysis Plan and Statistical Analysis) of the clinical study protocol (version 3.0, dated 30July2021), and is prepared in compliance with International Conference on Harmonisation (ICH) E9. Furthermore, this SAP contains definitions for analysis sets, derived variables, and statistical methods and data presentations for the analysis of efficacy and safety endpoints.

2. Objectives

2.1. Primary Objective

The primary objective for Part 1 of the study is to evaluate the safety of niclosamide administered to subjects with COVID-19.

The primary objective for Part 2 of the study is to evaluate the effect of niclosamide in addition to standard of care (SoC) compared to placebo in addition to SoC on fecal clearance of SARS-CoV-2 RNA.

2.2. Secondary Objective

The secondary objective of the study is to evaluate the clinical efficacy, safety, and tolerability of oral niclosamide in addition to SoC compared to placebo in addition to SoC.

2.3. Exploratory Objective

The exploratory objectives include characterization of the effect of niclosamide on disease progression and severity 4 and 6 months after starting treatment, and possible genotypic resistance analysis using the nasopharyngeal swabs, and/or stool samples.

3. Investigational Plan

3.1. Overall Study Design and Plan

[figure not shown]
This a 2-part, 2-arm, Phase 2, multicenter, randomized, double-blind, placebo-controlled study in adults with COVID-19. Subjects will be recruited and randomized to niclosamide oral formulation plus SoC or placebo matching niclosamide tablets plus SoC. The study will initiate with Part 1 and, upon safety review, the study may proceed to Part 2.

Part 1 will enroll approximately 9 subjects. After treatment is concluded for all 9 subjects, a DMC will review the safety data and determine if the study may proceed to Part 2 or if additional subjects are needed to assess tolerability of the study drug. If additional subjects are needed, approximately 9 more subjects will be enrolled in Part 1, and then the DMC will meet again after all subjects are treated to determine if the study may proceed to Part 2.

Part 2 will enroll up to approximately 150 subjects receiving at least 1 dose of study treatment.

Each part will include 2 study arms with randomized enrollment. Randomization of subjects in Part 2 will be stratified by age and sex. An overview of the study design is shown in Figure 1 and the Schedule of Assessments for the study is detailed in [Appendix 16.1](#).

Figure 1: Study Design

3.2. Study Endpoints

3.2.1. Primary Endpoint

The primary endpoint of Part 1 is summarization of safety (AEs, clinical laboratory results, and vital signs) from Day 1 (first dose) to Day 43 comparing the niclosamide arm to placebo arm.

The primary endpoint of Part 2 is time to fecal viral RNA clearance for subjects with a positive Day 1 stool test assessed by RT-qPCR from Day 1 (first dose) to Day 43 in the niclosamide arm compared to the placebo arm.

3.2.2. Secondary Endpoints

The secondary endpoints will all compare the niclosamide arm to the placebo arm. These secondary endpoints will be assessed for both Part 1 and Part 2 from Day 1 (first dose) to Day 43, as applicable.

- **Gastrointestinal Efficacy Secondary Endpoints**

- a) Part 1: Time to fecal viral RNA clearance for subjects with a positive Day stool test for SARS-CoV-2 assessed by RT-qPCR.
- b) Time from the first dose of study treatment to the first formed stool (this formed stool must have been followed by a non-watery stool) in subjects with loose or watery stool (Bristol Stool Scale Types 6-7) on Day 1.
- c) Time from the first dose of study treatment to the last loose or watery stool in subjects with loose or watery stool (Bristol Stool Scale Types 6-7) on Day 1.
- d) Proportion of subjects administered any anti-diarrheal agent from the first dose of study treatment to Day 8, first dose of study treatment to Day 15 and from Day 16 to 29.
- e) Time from the first dose of study treatment to improvement of abdominal symptoms in subjects with abdominal symptoms on Day 1.
- f) Proportion of patients with a negative Day 1 stool test for SARS-CoV-2 who acquire SARS-CoV-2 in stool through Day 43.

- **Systemic and Respiratory Efficacy Secondary Endpoints**

- g) Proportion of subjects with each clinical severity score as recommended by the WHO for COVID-19 studies by study visit.
- h) Total duration, type of administration (e.g., mean increased room oxygen, nasal tubes, ventilator, or ECMO), and quantity of supplemental oxygen treatment, whenever possible.
- i) Body temperature and proportion of subjects with normal body temperature by study visit. Criteria for normalization was temperature: $\leq 36.9^{\circ}\text{C}$ axillary, $\leq 37.4^{\circ}\text{C}$ oral, $\leq 37.8^{\circ}\text{C}$ rectal, and $\leq 37.5^{\circ}\text{C}$ tympanic ([Geneva et al., 2019](#)).
- j) Proportion of subjects with normal blood oxygen saturation by pulse oximeter (SaO₂) $>90\%$ on room air by study visit.
- k) Proportion of subjects admitted to the intensive care unit (ICU) and length of ICU stay.
- l) Time to nasopharyngeal viral clearance assessed by RT-PCR.
- m) Proportion of subjects requiring hospitalization and duration of hospitalization.

- **Safety and Tolerability Secondary Endpoints**

- n) All-cause mortality 6 weeks after randomization.
- o) Proportion of subjects with treatment-emergent adverse events (TEAEs) leading to study drug discontinuation.
- p) Serious adverse events (SAEs) coded by system organ class (SOC) and preferred term (PT) using the Medical Dictionary for Regulatory Activities (MedDRA).
- q) Clinically significant changes in laboratory measurements.
- r) Clinically significant changes in vital sign measurements.

3.2.3. Exploratory Endpoints

- s) All-cause mortality 4 months and 6 months after randomization.
- t) Proportion of subjects with recurrence of COVID-19 symptoms after Day 43 at 4 months and 6 months after randomization.
- u) Proportion of subjects with persistence of COVID-19 symptoms beyond Day 43 at 4 months and 6 months after randomization.
- v) Proportion of subjects with new hospitalization or rehospitalization due to COVID-19 at 4 months and 6 months after randomization.
- w) Summarization of genotypic resistance analysis data.

3.3. Treatments

The chemical name of niclosamide is 5-chloro-N-(2-chloro-4-nitrophenyl)-2-hydroxybenzamide. The IMPs are in the form of white yellowish oval 400-mg uncoated immediate-release (IR) tablets containing the active ingredient micronized niclosamide or a matched placebo.

Subjects who are able to comply with the oral treatment must take, for each administration, 1 tablet (400-mg niclosamide or placebo) TID for 14 days. Treatment may begin at any time of day; if only 1 or 2 doses are administered on Day 1, the planned total number of doses should be administered (42 total doses) and the final doses may be administered on Day 15. The total study duration for a subject will not be extended if the final dose occurs on Day 15 for this reason.

4. General Statistical Considerations

Continuous data will be described using descriptive statistics (i.e., number of subjects, mean, standard deviation, median, 25th percentile, 75th percentile, minimum, and maximum). Unless otherwise specified, minimum and maximum will be displayed to the same level of precision as reported. Mean and median will be displayed to one level of precision greater than the data collected. Standard deviation (SD) and standard error (SE) will be displayed to two levels of precision greater than the data collected. If the precision of the values being summarized are too large (e.g., 3 or more decimal places), then limit the precision to two decimal places and follow the rules previously stated above. If n=0, then display n and leave all other statistics blank. If n=1, then display “N/A” for SD and SE.

Categorical data will be described using the subject count and percentage in each category. When count data are presented, the percentage will be suppressed when the count is zero. A row denoted “Missing” will be included in count tabulations where specified on the shells to account for dropouts and missing values where applicable. The denominator for all percentages will be

the number of subjects in that treatment within the analysis set of interest, unless otherwise specified. Non-zero percentages will be rounded to one decimal place, except 100% will be displayed without any decimal places.

All subject data collected at scheduled and unscheduled visits, excluding data collected in the daily diary, will be presented in individual subject data listings. Dates will be shown in subject listings as they have been recorded. Data listings will be sorted by treatment group, subject identification number, date/time and visit where applicable. The treatment group (randomized) as well as subject's sex and age will be stated on each listing where applicable. Unless otherwise stated, data listings will be based on all subjects randomized. When no data are available for a table or listing, an empty page with the title will be produced with suitable text (e.g., "There are no records for this table/listing.").

Unless otherwise specified, baseline will be defined as the last non-missing assessment prior to or on the date that the first dose of treatment is taken. For subjects who are randomized, but not treated, the baseline will be defined as the last non-missing assessment prior to or on the date of randomization. Assessments from both scheduled and unscheduled visits will be used to determine baseline. The date of first and last dose will be collected on the End of Treatment eCRF.

Study day will be calculated relative to the first dose date:

- Day 1 is defined as the first dose date
- Assessments before the first dose date: Study Day = Assessment Date – First Dose Date
- Assessments after the first dose date: Study Day = Assessment Date – First Dose Date +1

Summaries or analyses by study visit will be based on data collected at scheduled visits (i.e., nominal visits as collected on eCRF) and data from unscheduled visits will not be included. Efficacy analyses for time to viral clearance or clinical improvement will include data from both scheduled and unscheduled visits. Laboratory treatment emergent summaries will also include data from both scheduled and unscheduled visits.

A two-sided hypothesis test will be used at a significance level of 0.05 for comparison between the niclosamide and the placebo group for the primary efficacy analysis. All other statistical analyses will also be performed using a two-sided hypothesis test at a nominal significance level of 0.05. No adjustment for Type I error will be made for multiple comparisons. Models will include stratification factors, age (<65 years or ≥65 years) and sex (female or male), unless an insufficient amount of data exists where convergence or the analysis cannot be performed.

Confidence intervals will be presented as two-sided 95% CI for the primary efficacy analysis secondary efficacy analyses. P-values will be rounded to three decimal places. If a p-value is less than 0.001 it will be reported as "<0.001." If a p-value is greater than 0.999 it will be reported as ">0.999." For analyses where convergence or the analysis cannot be performed, "NC" (not calculable) will be presented.

For all Tables, Listings, and Figures, treatment group will be labelled as follows: "Niclosamide + SoC" and "Placebo + SoC". All analyses will be conducted using SAS Version 9.4 or higher.

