10.2 Day 1: Treatment

The following procedures and tests will be performed on Day 1. If screening and Day 1 occur on the same day, assessments completed for screening are not required to be repeated on Day 1.

- Pre-dose
 - Confirmation of eligibility
 - Changes in the medical history and concomitant medications
 - Stool sample for the central laboratory
 - Clinical assessment of diarrhea (including anti-diarrheal agents)
 - Nasopharyngeal swab for the central laboratory
 - Laboratory assessments:
 - Central: Obtain samples for central laboratory.
 - Local: Any other laboratory tests may be conducted for the physician's safety assessment according to the local practice and patient's clinical needs.
 - Overall clinical assessment
- Randomization by means of an IWRS (randomization should occur after eligibility is confirmed, including all required laboratory tests)
- Administration of first dose and other TID doses, as they apply for the time of day
- Part 1 patients, who are not hospitalized, will be observed for approximately 30 minutes after receiving their first dose.
- Daily diary
- AE monitoring

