9.2. Clinical Laboratory Evaluations

Safety laboratory tests include chemistry and hematology on Days 1, 8, 15, 29, and 43 and will be performed by a central laboratory. All summaries will be based on the units provided by the central laboratory; no conversion will be made.

Summary tables displaying observed values and changes from baseline will be presented for numeric clinical laboratory tests by treatment group for subjects in the Safety set. Changes from baseline to each scheduled post-baseline visit (Days 8, 15, 29, and 43) will be presented. Box-and-whisker plots will also be displayed for each laboratory test at baseline and each scheduled post-baseline visit by treatment group.

All safety laboratory data will be included in separate listings and all test values outside the normal range will be flagged.

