9.3 Vital Signs

Vital signs will be measured on Days 1, 4, 8, 15, 22, 29, 36, and 43. Vital signs include systolic and diastolic blood pressure (mmHg), pulse rate (beats/min), blood oxygen saturation SpO₂, and temperature (°C) with method of measurement (axillary, oral, rectal, or tympanic).

Summary tables displaying observed values and changes from baseline will be presented for numeric vital sign data by treatment group for subjects in the Safety set. Changes from baseline to each scheduled post-baseline visit (Days 4, 8, 15, 22, 29, 36, and 43) will be presented.

All vital sign data will also be presented in a listing.

10. Exploratory Analysis

Exploratory analyses will be conducted on exploratory data collected at the Month 4 and Month 6 visits during the long term follow-up and will be included as the End of Study Final Analysis in an addendum to the main CSR.

All exploratory analyses will be performed using the FAS and will be presented separately for Part 1 and Part 2 of the study unless otherwise specified. Due the exploratory nature of these analyses, only descriptive summary statistics will be provided by treatment group and no inferential statistical tests will be performed.

All exploratory data including deaths will also be presented in separate listings.

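### The SAP sets baseline by date of first dose rather than by time, so an unscheduled Day 1 reading taken after dosing could replace the scheduled pre-dose value

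*SAP*

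**What the plan says.** SAP Section 4 (General Statistical Considerations) gives the general rule. Baseline is the "last non-missing assessment prior to or on the date that the first dose of treatment is taken", and "Assessments from both scheduled and unscheduled visits will be used to determine baseline". The rule applies unless another section says otherwise. Sections 9.2 (laboratory), 9.3 (vital signs), 8.2.5 (abdominal symptoms) and 8.3.1 (WHO score) all work from baseline and give no different definition of it.

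Protocol 10.2 lists the scheduled Day 1 swab, stool, laboratory, diarrhea and overall clinical assessments under the pre-dose heading. Dosing follows, at any time of day, and more than one dose can fall on Day 1. Non-hospitalized Part 1 patients "will be observed for approximately 30 minutes after receiving their first dose".

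For summaries by visit, SAP Section 4 states that "data from unscheduled visits will not be included". The vital-sign tables therefore run as follows: "Changes from baseline to each scheduled post-baseline visit (Days 4, 8, 15, 22, 29, 36, and 43) will be presented". For laboratory tests: "Changes from baseline to each scheduled post-baseline visit (Days 8, 15, 29, and 43) will be presented".

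SAP 9.1 counts an adverse event as treatment-emergent if it starts or worsens on or after the first-dose date. SAP 3.2.1 includes vital signs and laboratory results in the Part 1 primary safety endpoint.

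**The concern.** A baseline should precede treatment. This rule uses the calendar date, takes the latest value on that date and admits unscheduled readings, so nothing in it separates a Day 1 value before the dose from one after it. Unscheduled same-day readings are not random either: staff tend to repeat a measurement when something has happened.

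The SAP is also inconsistent about Day 1. An adverse event after dosing on that date is treatment-emergent, while a measurement made at the same moment can serve as the pre-treatment reference.

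At stake are the change-from-baseline tables for vital signs, which matter most in Part 1, where they belong to the primary endpoint and the arms are very small. In Part 2, two inferential secondary analyses also depend on baseline: time to improvement of abdominal symptoms and time to improvement of WHO score. Each counts a reduction of one level or one point as an event.

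**Working it through.** The documents give no figure that depends on the baseline definition, so there is nothing to reproduce. The check traces the rule through the tables that use it.

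**Effect on one subject.** Let the pre-dose value be b and an unscheduled post-dose Day 1 value be b + d. Change at a later visit is the visit value minus baseline.

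| State at the later visit | Visit value | Change, pre-dose baseline | Change, SAP baseline |
|---|---|---|---|
| Effect persists | b + d | +d | 0 |
| Effect resolved | b | 0 | −d |

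In both rows the SAP rule moves the subject's change by −d. The first row is masking; the second is a false change in the opposite direction. Because by-visit tables leave out unscheduled values, the Day 1 post-dose reading enters them only as the baseline.

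**Effect on an arm mean.** With one affected subject among n, the shift in mean change is −d/n.

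- Part 1: about 9 patients randomized 2:1 (Protocol 9.1.1) gives 9 × 2/3 = 6 active patients.
- Part 2: about 150 patients randomized 1:1 (Protocol 9.1.2) gives 150/2 = 75 per arm.
- Size of d: the documents give none. I assume 20 mmHg, with 10 to 30 as a range.

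| d (assumed) | Part 1 active arm, d/6 | Part 2 arm, d/75 |
|---|---|---|
| 10 | 1.7 | 0.13 |
| 20 | 3.3 | 0.27 |
| 30 | 5.0 | 0.40 |

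The documents do not say how often such a reading would occur, so these are shifts per affected subject and not an expected bias.

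**Effect on the improvement endpoints.** Suppose abdominal symptoms are mild before the dose, are recorded as moderate after it on Day 1, and are mild again at Day 4. Against the pre-dose value there is no improvement at Day 4. Against the SAP baseline there is a one-level reduction, which SAP 8.2.5 counts as improvement. The same reasoning applies to a one-point change in WHO score under SAP 8.3.1. Protocol 6.1 lists nausea, vomiting and abdominal pain among the reported reactions to niclosamide, so a first-dose side effect could be scored as benefit. This needs a second, post-dose severity record on Day 1, which the protocol does not schedule.

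**Which data can be affected.**

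- *Vital signs:* exposed, but only if the extra reading is entered. Footnote 5 of the Schedule of Assessments requires CRF entry of Part 1 vital signs only when the full clinical assessment is due, and the Day 1 full assessment is pre-dose.
- *Laboratory:* SAP 9.2 says "Safety laboratory tests include chemistry and hematology on Days 1, 8, 15, 29, and 43 and will be performed by a central laboratory". The Day 1 central sample is pre-dose, and Protocol 10.2 places additional tests for the physician's safety assessment at the local laboratory. An ad hoc test after a reaction is therefore unlikely to reach these tables.
- *Laboratory treatment-emergent summaries:* Section 4 says "Laboratory treatment emergent summaries will also include data from both scheduled and unscheduled visits", and there a post-dose value used as baseline could not count as emergent. SAP 9.2 describes no such table, so this remains hypothetical.

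**The case against.** A reader might infer that the rule hides first-dose reactions from the safety evaluation. The documents do not support that, for four reasons.

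- The change tables begin at Day 4 for vital signs and Day 8 for laboratory tests. A reaction that resolves on Day 1 would be absent from them under any baseline rule. Masking in the strict sense needs an effect that lasts to those visits.
- A reaction reported as an adverse event on Day 1 is a TEAE and appears in those tables. All data except the diary, scheduled or not, are listed by subject.
- The Part 1 decision rests on the DMC's medical judgment and requires no specific statistics (Protocol 12.6, SAP Section 11). A shift of a few mmHg in a mean of six would not drive it, and the descriptive summaries also show quartiles and extremes.
- The 30-minute observation in Protocol 10.2 orders no measurement, so it does not show that a post-dose value would be recorded.

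All four stand, and they limit the size of the problem. None makes the rule correct: if a post-dose Day 1 value is in the database, the text as written makes it the baseline, and the scheduled pre-dose value is set aside.

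**Conclusion.** The point holds as a small defect in a definition. Read literally, SAP Section 4 lets an unscheduled post-dose Day 1 value become baseline, which makes that subject's later changes wrong at every scheduled visit.

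The number of subjects is probably small and the exposure lies mainly in vital signs. The 3.3 mmHg (Part 1) and 0.3 mmHg (Part 2) figures rest on an assumed 20 mmHg shift in one subject. The effect on the WHO and abdominal-symptom analyses depends on a post-dose Day 1 record that the protocol does not call for. No power or alpha figure depends on the rule, and the primary efficacy endpoint is not defined by change from baseline. This is an inexpensive improvement, not a threat to the trial's conclusions.

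**What to change.** Replace the baseline sentence in SAP Section 4 with wording to this effect: baseline is the latest available assessment obtained before the first dose; on Day 1 the scheduled pre-dose assessment is used; an unscheduled Day 1 value is eligible only if its time or accompanying documentation shows that it preceded the first dose; all other unscheduled Day 1 values are treated as post-baseline.

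The cost is that sentence, a programming flag and a check of the few unscheduled Day 1 records. Some ambiguous values will not be used as baseline, but the scheduled pre-dose assessments already supply one. SAP Section 4 says that the date of first dose is collected and does not mention its time, so the sponsor should confirm whether time is captured. If it is not, the scheduled pre-dose assessment serves as the fallback. The change should be made before unblinding, so that no choice of baseline is made afterwards for the very patients who had a reaction.
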